2.2 SAMPLE SIZE DETERMINATION

Approximately 105 participants with ASD randomized in a 1:1:1 ratio between two active dosing regimens and placebo need to be recruited in order to obtain evaluable data from approximately 84 participants after 12 weeks of treatment. Evaluable data from 84 ASD participants provides at least 80% power to detect a mean difference between baseline and 12-week follow-up of 4.5 points on a Vineland $^{\text{TM}}$ -3 composite between any active treatment arm and the placebo arm with α = 0.10 error control (1-sided). The minimally detectable difference in this cohort is 2.7 points. It is assumed that the standard deviation of the differences between baseline and 12 weeks follow up is 8.0 points, that 20% of participants will not provide evaluable data, and that the participants recruited will consist of at most 25% low-functioning participants, at most 25% female participants. Because the purpose of this study is exploratory, no adjustment for comparison of multiple active doses to a single placebo arm is performed.

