4.2 PRIMARY, SECONDARY AND EXPLORATORY EFFICACY ANALYSIS

The primary efficacy analysis evaluates the mean change from baseline to 12 weeks of treatment as measured by the Vineland-3 ABC three-domain GSV composite. The difference in the mean change from baseline between each of the two active doses and placebo will be extracted as contrasts from the ANCOVA model.

The efficacy analyses of the secondary endpoints and of the CRRI total score evaluate the mean change from baseline to 12 weeks of treatment. The difference in the mean change from baseline of the two active doses and placebo will be extracted as contrasts from the ANCOVA model.

The efficacy analysis of CGI-I evaluates the overall score at 12 weeks of treatment. The difference of the two active doses and placebo will be extracted as contrasts from the ANCOVA model.

4.2.1 Definition of Primary Endpoint

The primary endpoint is Change from baseline to Week 12 in the Adaptive Behavior Composite score of the Vineland[™] Adaptive Behavior Scales, Third Edition (Vineland[™]-3), as defined in Section 1.1 of SAP (see Table 1).

4.2.2 Main Analytical Approach for Primary, Secondary, CRRI and CGI-I Endpoints

The analyses of primary, secondary, CRRI and CGI-I efficacy endpoints will include all participants in the Efficacy Analysis Population.

An analysis of covariance (ANCOVA) model will be used to compare treatment effects for the primary, secondary, CRRI and CGI-I efficacy endpoints across the overall Efficacy Analysis Population of adolescents and adults. The model will include treatment as main effect, individual age at screening, IQ, and baseline score as covariates. Treatment differences will be estimated together with their 80% confidence intervals as derived from the model and their associated p-values.

The ANCOVA model will be applied to change from baseline data y_{ij} of participants i, and treatment $j \in \{\text{placebo (reference)}, \text{low dose}, \text{high dose}\}\)$ as follows:

$$y_{ij}=\mu+t_i+a_i+IQ_i+BL_i+\epsilon_{ij}$$

where μ gives the overall endpoint mean change, followed by the fixed effect t which models the effect of treatment, age a, IQ, the endpoint baseline value BL, and ϵ , which gives the overall error term with $N(0, \sigma_{\epsilon}^2)$.

Table 8 Efficacy Statistical Analysis Methods

Endpoint	Statistical Analysis Methods
Primary	ANCOVA
Secondary	
CRRI, CGI-I	

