4.3 SUPPORTIVE EXPLORATORY EFFICACY ENDPOINTS ANALYSES

Additional exploratory analyses will be performed in a descriptive manner for continuous endpoints Vineland-3, RBS-R, CRRI, CGI, AASP, PRAS-ASD, BAI, SSP-2, PedsQL™, and PROMIS per treatment arm comprising baseline values, (up to) week 12 values and change from baseline to (up to) week 12 values.

For endpoint CGI, analyses will be performed to get the proportion of subjects in each of the rating categories per treatment arm and per time point.

For the assessment of differences between each Alogabat group and placebo regarding the CGI-I overall score at week 12, a mixed-effects MMRM analysis incorporating data up to 12 weeks of treatment will be used to utilize all the data collected over time with consideration of the variance-covariance matrix of the repeated measures. The model will include the CGI-I overall score as the dependent variable. The effects in the model will include independent variables of the fixed, categorical effects of treatment, assessment weeks relative to the first dose of study medication (i.e., time), and treatment-by-time interaction, along with covariates of the baseline value, age at screening and IQ at baseline. Time will be treated as the repeated variable within a subject. An unstructured variance-covariance structure will be applied to model the within-subject errors.

For the primary, secondary, CRRI and CGI-I endpoints, the ANCOVA will be repeated to model change from baseline data y_{ij} of participants i, and treatment $j \in \{\text{placebo}\}\$ (reference), low dose, high dose) incorporating interactions to the model as follows:

$$y_{ij}=\mu+t_j+a_i+IQ_i+t_j*IQ_i+BL_i+\epsilon_{ij}$$

and

$$y_{ij}=\mu+t_j+a_i+IQ_i+t_j*a_i+BL_i+\epsilon_{ij}$$

where μ gives the overall endpoint mean change, followed by the fixed effect t which models the effect of treatment, age a, IQ, the interactions t^*IQ and t^*a respectively, the endpoint baseline value BL, and ε , which gives the overall error term with $N(0, \sigma_{\varepsilon}^2)$.

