4.5.3 Biomarker Analyses

Resting state EEG is recorded up to five times per patient: Pre-baseline, day 1 pre-dose, day 1 post-dose, week 2 post-dose (optional recording) and week 12 post-dose. EEG beta power is defined as the total power in the 13-30 Hz range averaged over the fronto-central channels Fz and Cz.

To estimate pharmacodynamic effects, beta power for post-dose recordings are normalized with baseline beta power to estimate relative change. Baseline beta power is defined as the average of the pre-baseline and day 1 pre-dose values. For each post-dose recording (day 1, week 2, week 12) and dose level, the mean change and SD of change will be reported. Additionally, two-tailed two sample t-tests comparing placebo to

each treatment arm will be performed for each post-dose recording. Hereby the null-hypothesis of no difference in beta power with Alogabat treatment compared to placebo will be rejected if the p-value resulting from a two-sided t-test is < 0.1.

It will also be examined whether baseline beta power predicts clinical response. The hypothesis is that clinical efficacy increases as beta power decreases (patients with lower baseline beta power benefit more from alogabat than patients with higher baseline beta power). To this end beta power is normalized with power outside the beta range. The Baseline value is defined as the average of the pre-baseline and day 1 pre-dose values. The Pearson correlation coefficient between baseline beta power and change from baseline clinical efficacy scores will be computed for each active treatment arm and placebo. For active treatment arms the p-value will be derived from a two-sided test with null-hypothesis: r = 0. The null hypothesis will be rejected if the two-sided p-value is < 0.2. The test will be performed for the clinical efficacy endpoints Vineland-3 ABC GSV composite, Vineland-3 Socialization GSV composite, RBS-R total, and CRRI total.

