t_<>	Efficacy	Correlation between Baseline EEG beta power and clinical efficacy	
t_pql_tot_cfb	Efficacy	PedsQL™ Total Score Change from Baseline	
t_pql_cfs_cfb	Efficacy	PedsQL [™] Cognitive Functioning Score Change from Baseline	
g_cgii	Efficacy	CGI-I Overall Score over Time	
g_cgis	Efficacy	CGI-S Overall Score over Time	
g_forest	Efficacy	Vineland-3 ABC GSV composite	

	•		
		by Geographic Region with 80% CI	
g_forest	Efficacy	Vineland-3 ABC GSV composite by Rater Change with 80% CI	
g_forest	Efficacy	Vineland-3 ABC GSV composite by Site Type with 80% CI	
g_forest	Efficacy	Vineland-3 ABC GSV composite by Age Category with 80% CI	
g_forest	Efficacy	Vineland-3 ABC GSV composite by IQ Category with 80% CI	
g_forest	Efficacy	RBS-R total score by Geographic Region with 80% CI	
g_forest	Efficacy	RBS-R total score by Rater Change with 80% CI	
g_forest	Efficacy	RBS-R total score by Site Type with 80% CI	
g_forest	Efficacy	RBS-R total score by Age Category with 80% CI	
g_forest	Efficacy	RBS-R total score by IQ Category with 80% CI	
g_forest	Efficacy	RBS-R total score by Diagnosis of Anxiety at Baseline with 80% CI	
g_forest	Efficacy	RBS-R total score by Sex with 80% CI	
g_forest	Efficacy	CRRI total score by Sex with 80% CI	
g_forest	Efficacy	CGII (RRB domain) by Sex with 80% CI	
g_forest	Efficacy	BAI total score by Diagnosis of Anxiety at Baseline with 80% CI	

Certificate Of Completion

Envelope Id: 00A25604873540C595AE83AF56584F0E

Subject: Complete with Docusign: BP41316_SAP_V02.pdf

Source Envelope:

Document Pages: 51 Signatures: 1 Certificate Pages: 4 Initials: 0

AutoNav: Enabled

Envelopeld Stamping: Disabled

Time Zone: (UTC+01:00) Amsterdam, Berlin, Bern, Rome, Stockholm, Vienna

Status: Completed

Envelope Originator:

[name]

IP Address:

Record Tracking

Status: Original

6/28/2024 1:54:12 PM

Holder:

Location: DocuSign

Signer Events

Statistician

F. Hoffmann-La Roche

Security Level: Email, Account Authentication

(Required)

Signature

Timestamp

Sent: 6/28/2024 1:54:56 PM Viewed: 6/28/2024 1:55:15 PM Signed: 6/28/2024 1:55:35 PM

Signature Adoption: Pre-selected Style Signature ID:

With Signing Reasons (on each tab):

10EC3CF5-F664-481F-BAE0-AD933DC0A009

Using IP Address:

With Signing Authentication via DocuSign password

I approve this document

Electronic Record and Signature Disclosure:

Accepted: 11/2/2020 2:09:16 PM

ID: 102e05f3-7156-49ba-9ce4-508e079f28ec

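### The baseline beta-power analysis is meant to show who benefits more from alogabat, but it tests only r = 0 within each active arm and never formally compares with placebo

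*SAP*

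**What the plan says.** SAP 4.5.3 (Biomarker Analyses) asks whether baseline beta power predicts clinical response and spells out the direction: "patients with lower baseline beta power benefit more from alogabat than patients with higher baseline beta power". The statistic is a Pearson correlation between baseline beta power and the change in clinical score, which "will be computed for each active treatment arm and placebo". Only the active arms get a p-value: "For active treatment arms the p-value will be derived from a two-sided test with null-hypothesis: r = 0". The rule is "The null hypothesis will be rejected if the two-sided p-value is < 0.2". It applies to four endpoints: Vineland-3 ABC GSV, Vineland-3 Socialization GSV, RBS-R total and CRRI total.

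Other sections do not supply a comparison with placebo on this question:

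- SAP 4.2.2.1 has no beta-power subgroup.
- SAP 4.3 repeats the ANCOVA "incorporating interactions to the model as follows", but the two models shown are treatment by IQ and treatment by age.
- SAP Appendix 1 lists one relevant output, "Correlation between Baseline EEG beta power and clinical efficacy".
- The placebo t-tests in SAP 4.5.3 concern post-dose change in beta power, which is a pharmacodynamic question.
- Protocol 9.4.5 plans only listings and descriptive summaries for biomarkers.

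**The concern.** The hypothesis is about a predictive marker: the relation between beta power and outcome should differ between alogabat and placebo. The test is about association within a treated arm. Such an association also arises if beta power is merely prognostic, so that it tracks change over 12 weeks whatever the treatment, or if it tracks placebo response or regression to the mean. A rejection alone cannot separate these explanations.

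The SAP Introduction gives the biomarkers a role in a first attempt to find responder subgroups. What is at stake is carrying forward, as a selection marker for alogabat, a measure that says nothing specific about the drug.

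**Working it through.** **Inputs.** SAP 2.1 assumes at least 28 evaluable per arm, which agrees with SAP 2.2 (84/3 = 28; 105 × 0.8 = 84). The test level is two-sided 0.2 (SAP 4.5.3). The documents give no correlation for beta power, so |r| from 0 to 0.4 is assumed. A second case of 20 usable EEGs per arm is also an assumption.

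**The plan's own figure.** None is given for this test. The primary sizing reproduces closely: SE = 8.0 × √(2/28) = 2.138; power = Φ(4.5/2.138 − 1.2816) = Φ(0.823) = 79.5%, against the stated 80%; minimally detectable difference = 1.2816 × 2.138 = 2.74, against the stated 2.7.

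**Critical correlation.** |r| = t/√(n − 2 + t²), with t the 0.90 quantile on n − 2 df.

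- n = 28: 1.315/√(26 + 1.729) = 0.250
- n = 20: 1.330/√(18 + 1.769) = 0.299

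**Same correlation in every arm, so no differential benefit.** By Fisher's z with n = 28, the within-arm rejection probability is Φ(5·atanh r − 1.2816) + Φ(−5·atanh r − 1.2816), where 5 = √(28 − 3). At r = 0.3 this is Φ(0.266) + Φ(−2.829) = 0.605 + 0.002 = 0.607. Simulation (20,000 trials per cell) gives the following. The interaction is the treatment by beta-power contrast of one dose with placebo, one-sided 0.10 in the predicted direction, from an ANCOVA with three covariates and 3n − 9 residual df.

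| Shared abs. r | Within-arm test, n = 28 | Interaction, n = 28 | Active rejects and placebo would not, n = 28 | Within-arm test, n = 20 |
|---|---|---|---|---|
| 0 | 20.0% | 10.0% | 16.0% | 19.7% |
| 0.1 | 25.8% | 10.0% | 19.2% | 24.2% |
| 0.2 | 41.7% | 9.8% | 24.8% | 35.1% |
| 0.3 | 62.2% | 10.4% | 23.9% | 51.7% |
| 0.4 | 81.2% | 10.2% | 14.9% | 70.5% |

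The within-arm column counts both directions and the interaction column only one. On one scale, counting only predicted-direction rejections when the shared correlation has the predicted sign, the within-arm test gives about 22%, 39%, 62% and 81% at |r| = 0.1 to 0.4, against about 10% for the interaction. If the shared correlation has the opposite sign, predicted-direction rejection is about 1% at |r| = 0.2: Φ(−1.014 − 1.2816) = 0.011.

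**Correlation in the active arms only, so the hypothesis is true.**

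| Abs. r in active arms | Interaction, n = 28 | Within-arm, n = 28 | Interaction, n = 20 | Within-arm, n = 20 |
|---|---|---|---|---|
| 0.2 | 29.1% | 41.8% | 24.7% | 35.5% |
| 0.3 | 42.1% | 61.7% | 34.4% | 52.0% |
| 0.4 | 58.2% | 81.2% | 47.4% | 70.5% |

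**Sensitivity (n = 28, |r| = 0.2 and 0.4).** With covariates related to outcome, interaction error is 10.4% and 10.1%, and power 29.0% and 57.8%. With covariates also related to beta power, error is 10.2% and 9.8%, and power 28.0% and 57.7%.

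**The case against.** The strongest reply is that the placebo coefficient will be on the page. A careful reader would set it beside the active arms, and the SAP does not claim that an active-arm rejection alone proves a predictive marker. Read jointly, the excess is modest: rejection in an active arm with none in placebo occurs in 15% to 25% of trials under a shared correlation, against 16% with no association at all. This stands as a limit on the size of the problem. It does not close the gap, because the SAP gives the placebo coefficient no p-value, interval or reading rule. Setting significant beside not significant is also not a test of the difference.

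Other points on that side stand in part:

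- A shared correlation in the unpredicted direction would contradict the hypothesis rather than mimic support. The risk is therefore confined to one sign, and the documents give no indication of which.
- The 20-per-arm case has no basis in the documents. The EEG exclusions in SAP section 3 concern post-treatment recordings, not the baseline ones used here.
- An output title does not show what a table contains, so the Appendix 1 entry is weak evidence. The text of SAP 4.5.3 carries the point.
- Protocol 9.1 describes the study as hypothesis-generating, and a sensitive within-arm screen is a defensible pilot choice. Part of its higher rejection rate, however, comes from not subtracting the placebo slope, which is the quantity the hypothesis concerns.

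**Conclusion.** The concern holds. The stated hypothesis is one of differential benefit, and the only rule attached to it cannot distinguish that from a prognostic association. With 28 per arm and a shared correlation of 0.2 to 0.4, each active-arm test rejects in roughly 40% to 80% of trials although the marker does not predict benefit from alogabat. If the shared correlation is 0.1 or less, the excess over the nominal 20% is at most about 6 points. These figures rest on assumed correlations and, in the main runs, on covariates unrelated to outcome and beta power; the interaction results changed little when that was relaxed.

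The priority is low. The primary and secondary analyses and the decision criteria in SAP 2.1 rest on the ANCOVA and are unaffected.

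**What to change.** Extend the ANCOVA of SAP 4.2.2, in which "The model will include treatment as main effect, individual age at screening, IQ, and baseline score as covariates", by baseline beta power and treatment by beta power. This is the form SAP 4.3 already uses for age and IQ. For each of the four endpoints, report the slope difference of each dose minus placebo with its 80% CI.

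If a decision rule is kept, use one-sided 0.10 in the predicted direction. That is the same cut-off as two-sided 0.2 on that side and matches the level in SAP 2.2. The predicted slope difference is negative for Vineland-3 ABC GSV and Socialization GSV, where higher is better, and positive for RBS-R total and CRRI total, where higher is worse. Keep the three Pearson coefficients as description. The within-arm p-values may stay if labelled as not testing differential benefit.

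The cost is SAP wording, one main effect and two contrasts per endpoint, with no new data. Power per contrast falls to about 29%, 42% and 58% at |r| = 0.2, 0.3 and 0.4 with 28 per arm, and the intervals will be wide. Error is about 10% per contrast and about 17% for at least one of the two doses on one endpoint. Over four endpoints it could reach 1 − (1 − 0.17)⁴, about 53%, if they were independent, and less because they are correlated. The result therefore remains hypothesis-generating.

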4.6 INTERIM ANALYSES

Two interim safety analyses are planned for this study. The first interim analysis of accumulated safety, tolerability and PK will be performed once approximately 18 high-functioning adults have completed 6 weeks of treatment. The aim of this analysis is to evaluate the safety, tolerability, and PK in high-functioning adults before allowing the recruitment of the adolescents and low-functioning adult participants.

A second interim analysis of PK and accumulated safety and tolerability will be conducted once approximately 12 adolescents have completed 2 weeks of treatment. The aim of this analysis is to enable internal decisions to inform the design and dose selection for the adolescent participants and additional studies in the program.

The CSR will document all interim analyses that occurred. All interim analyses will be performed and interpreted by members of the IMC, external experts (SOC), and appropriate senior management personnel. IMC and SOC members will be unblinded at the individual participant level, sponsor senior management will be unblinded at the treatment group level. Access to treatment assignment information will follow the Sponsor's standard procedures.

The "IMC Agreement" will describe the planned interim analyses in detail.



APPENDIX 1

LIST OF PLANNED OUTPUTS FOR EFFICACY AND SAFETY

Provisional Output Name	Population	Title	
l_ae_gloss	Safety	Glossary of Adverse Event Preferred Terms and Investigator-Specified Adverse Event Terms	
I_ae	Safety	Listing of Adverse Events	
I_ae_postdose	Safety	Listing of new onset AEs after last dose of study medication	
l_ae_disc	Safety	Listing of Adverse Events Leading to Study Treatment Discontinuation	
l_cm_gloss	Safety	Glossary of Concomitant Medication Class, Preferred Name, and Investigator-Specified Terms	
I_cm	Safety	Listing of Concomitant Medication	

l_cssrs	Safety	Columbia-Suicide Severity Rating Scale (C-SSRS)	
l_ds	Safety	Listing of Patients who Discontinued from Study	
l_dv	Safety	Listing of Major Protocol Deviations	
I_eg	Safety	Listing of ECG Data	
l_ex_ti	Safety	Listing of Drug Administration and Dosing Time	
l_mh_gloss	Safety	Glossary of Medical History Coded Terms	
I_mh	Safety	Listing of Medical History	
l_vs	Safety	Listing of Vital Signs	
t_ae_int	Safety	Adverse Events by Greatest Intensity	
t_ae_oview	Safety	Safety Summary	
t_ae	Safety	Adverse Events	
t_cssrs	Safety	Columbia-Suicide Severity Rating Scale (C-SSRS)	
t_dm	Safety	Demographic and Baseline Characteristics	
t_ds	Safety	Patient Disposition	
t_eg_cfb	Safety	ECG Parameters Change from Baseline by Visit	
t_ess_cat	Safety	Epworth Sleepiness Scale (ESS) Total Score Categories	
t_ess_cfb	Safety	Epworth Sleepiness Scale (ESS) Change from Baseline by Visit	
t_ess_chad_c at	Safety	ESS for Adolescents Sleepiness Scale (ESS-CHAD) Total Score Categories	
t_ess_chad_cf b	Safety	ESS for Adolescents Sleepiness Scale (ESS-CHAD) Change from Baseline by Visit	
t_ex	Safety	Study Treatment Exposure	
t_kss_cfb	Safety	Karolinska Sleepiness Scale (KSS) Change from Baseline by Visit	
t_lb_abn_ls	Safety	Laboratory Abnormalities (Standardised parameters)	
t_lb_abn_nls	Safety	Laboratory Abnormalities (Non-Standardised parameters)	
t_lb_cfb_ls	Safety	Laboratory Tests and Change from Baseline by Visit (Standardised parameters)	

t_lb_cfb_nls	Safety	Laboratory Tests and Change from Baseline by Visit (Non-Standardised parameters)	
t_neuro_cfb	Safety	Neurocognitive Battery Change from Baseline by Visit	
t_sudden	Safety	Sudden Onset of Sleep Questionnaire	
t_vs_cfb	Safety	Vital Signs Change from Baseline by Visit	
l_ae_ser	Safety	Listing of Serious Adverse Events	
l_dm	Safety	Listing of Demographic and Baseline Characteristics	
l_lb_abn	Safety	Listing of Laboratory Abnormalities	
I_lb	Safety	Listing of Laboratory Data and Change from Baseline by Visit	
t_ae_pt	Safety	Adverse Events by Preferred Term	
t_ae	Safety	Adverse Events Related to Study Treatment	
t_cm	Safety	Medications Started after Baseline by Medication Class and Preferred Name	
t_cm	Safety	Medications Ongoing at Baseline by Medication Class and Preferred Name	
t_cm	Safety	Medications Completed Prior to Baseline by Medication Class and Preferred Name	
t_eg_abn	Safety	ECG Parameters outside Normal Limits Regardless of Abnormality at Baseline	
t_eg_abnbl	Safety	ECG Parameters outside Normal Limits Among Patients without Abnormality at Baseline	
t_eg_qtcf	Safety	QTcF Actual Values and Change from Baseline by Visit	
t_mh	Safety	Previous and Concurrent Medical History	
I_ae_nsaesi	Safety	Listing of Non-Serious Adverse Events of Special Interest	
t_ae_nsaesi	Safety	Non-Serious Adverse Events of Special Interest	
g_ex_hist	Safety	Histogram of Dosing Time	
g_vs_mean	Safety	Mean Plot from of Vital Sign Parameters Over Time with 95% CI	
g_vs_mean_cfb	Safety	Mean Change from Baseline Plot of Vital Sign Parameters Over Time with 95% Cl	

[figure not shown]
g_lb_mean_ls	Safety	Roche-Standardized Laboratory Data
g_lb_mean_nl s	Safety	Non-Standardized Laboratory Data
g_eg_mean	Safety	Mean Plot of ECG Parameters Over Time with 95% Cl
g_eg_mean_cfb	Safety	Mean Change from Baseline Plot of ECG Parameters Over Time with 95% CI
g_ess	Safety	ESS over Time
g_ess_cfb	Safety	ESS Change from Baseline over Time
g_kss	Safety	KSS over Time
g_kss_cfb	Safety	KSS Change from Baseline over Time
g_neuro	Safety	Neurocognitive Battery

[figure not shown]
t_vabs3_ancov	Efficacy	Vineland-3 ABC GSV Score ANCOVA no interactions
t_vabs3_ancov	Efficacy	Vineland-3 ABC GSV Score ANCOVA age interaction
t_vabs3_ancov a	Efficacy	Vineland-3 ABC GSV Score ANCOVA IQ interaction
t_vabs3_ancov a	Efficacy	Vineland-3 SOC GSV Score ANCOVA no interactions
t_vabs3_ancov a	Efficacy	Vineland-3 SOC GSV Score ANCOVA age interaction
t_vabs3_ancov a	Efficacy	Vineland-3 SOC GSV Score ANCOVA IQ interaction
t_vabs3_ancov a	Efficacy	Vineland-3 COM GSV Score ANCOVA no interactions
t_vabs3_ancov a	Efficacy	Vineland-3 COM GSV Score ANCOVA age interaction
t_vabs3_ancov a	Efficacy	Vineland-3 COM GSV Score ANCOVA IQ interaction
t_vabs_cfb	Efficacy	Vineland-3 ABC GSV Score Change from Baseline
t_vabs_cfb	Efficacy	Vineland-3 SOC GSV Score Change from Baseline
t_vabs_cfb	Efficacy	Vineland-3 COM GSV Score Change from Baseline
t_vabs_cfb	Efficacy	Vineland-3 DLS GSV Score Change from Baseline
t_vabs_cfb	Efficacy	Vineland-3 ABC Standard Score Change from Baseline
t_vabs_cfb	Efficacy	Vineland-3 SOC Standard Score Change from Baseline
t_vabs_cfb	Efficacy	Vineland-3 COM Standard Score Change from Baseline
t_vabs_cfb	Efficacy	Vineland-3 DLS Standard Score Change from Baseline
t_rbsr_ancova	Efficacy	RBS-R Total Score ANCOVA no interactions
t_rbsr_ancova	Efficacy	RBS-R Total Score ANCOVA age interaction
t_rbsr_ancova	Efficacy	RBS-R Total Score ANCOVA IQ interaction
t_rbsr_cfb	Efficacy	RBS-R Total Score Change from Baseline
t_rbsr_cfb	Efficacy	RBS-R Subscale Score (3FM) Change from Baseline

[figure not shown]
t_crri_ancova	Efficacy	CRRI Total Score ANCOVA no interactions	
t_crri_ancova	Efficacy	CRRI Total Score ANCOVA age interaction	
t_crri_ancova	Efficacy	CRRI Total Score ANCOVA IQ interaction	
t_crri_cfb	Efficacy	CRRI Total Score Change from Baseline	
t_crri_cfb	Efficacy	CRRI Subscale Score (5FM) Change from Baseline	
t_cgii_ancova	Efficacy	CGI-I Overall Score ANCOVA no interactions	
t_cgii_ancova	Efficacy	CGI-I Overall Score ANCOVA age interaction	
t_cgii_ancova	Efficacy	CGI-I Overall Score ANCOVA IQ interaction	
t_cgii_mmrm	Efficacy	CGI-I Overall Score MMRM	
t_cgii	Efficacy	CGI-I Overall Score	
t_cgii_cat	Efficacy	CGI-I Proportions per Rating Category	
t_cgis	Efficacy	CGI-S Overall Score	
t_cgis_cat	Efficacy	CGI-S Proportions per Rating Category	
t_bai_cfb	Efficacy	BAI Total Score Change from Baseline	
t_pras_cfb	Efficacy	PRAS-ASD Total Score Change from Baseline	
t_ssp_cfb	Efficacy	SSP-2 Summary Score Change from Baseline	
t_aasp_cfb	Efficacy	AASP Quadrant Summary Score Change from Baseline	
t_promis_cfb	Efficacy	PROMIS Sleep-Disturbance T-Score Change from Baseline	
t_promis_cfb	Efficacy	PROMIS Sleep Related Impairment T-Score Change from Baseline	
t_<>	Efficacy	Change from Baseline in EEG beta power	
t_<>	Efficacy	Correlation between Baseline EEG beta power and clinical efficacy	
t_pql_tot_cfb	Efficacy	PedsQL™ Total Score Change from Baseline	
t_pql_cfs_cfb	Efficacy	PedsQL [™] Cognitive Functioning Score Change from Baseline	
g_cgii	Efficacy	CGI-I Overall Score over Time	
g_cgis	Efficacy	CGI-S Overall Score over Time	
g_forest	Efficacy	Vineland-3 ABC GSV composite	

	•		
		by Geographic Region with 80% CI	
g_forest	Efficacy	Vineland-3 ABC GSV composite by Rater Change with 80% CI	
g_forest	Efficacy	Vineland-3 ABC GSV composite by Site Type with 80% CI	
g_forest	Efficacy	Vineland-3 ABC GSV composite by Age Category with 80% CI	
g_forest	Efficacy	Vineland-3 ABC GSV composite by IQ Category with 80% CI	
g_forest	Efficacy	RBS-R total score by Geographic Region with 80% CI	
g_forest	Efficacy	RBS-R total score by Rater Change with 80% CI	
g_forest	Efficacy	RBS-R total score by Site Type with 80% CI	
g_forest	Efficacy	RBS-R total score by Age Category with 80% CI	
g_forest	Efficacy	RBS-R total score by IQ Category with 80% CI	
g_forest	Efficacy	RBS-R total score by Diagnosis of Anxiety at Baseline with 80% CI	
g_forest	Efficacy	RBS-R total score by Sex with 80% CI	
g_forest	Efficacy	CRRI total score by Sex with 80% CI	
g_forest	Efficacy	CGII (RRB domain) by Sex with 80% CI	
g_forest	Efficacy	BAI total score by Diagnosis of Anxiety at Baseline with 80% CI	

Certificate Of Completion

Envelope Id: 00A25604873540C595AE83AF56584F0E

Subject: Complete with Docusign: BP41316_SAP_V02.pdf

Source Envelope:

Document Pages: 51 Signatures: 1 Certificate Pages: 4 Initials: 0

AutoNav: Enabled

Envelopeld Stamping: Disabled

Time Zone: (UTC+01:00) Amsterdam, Berlin, Bern, Rome, Stockholm, Vienna

Status: Completed

Envelope Originator:

[name]

IP Address:

Record Tracking

Status: Original

6/28/2024 1:54:12 PM

Holder:

Location: DocuSign

Signer Events

Statistician

F. Hoffmann-La Roche

Security Level: Email, Account Authentication

(Required)

Signature

Timestamp

Sent: 6/28/2024 1:54:56 PM Viewed: 6/28/2024 1:55:15 PM Signed: 6/28/2024 1:55:35 PM

Signature Adoption: Pre-selected Style Signature ID:

With Signing Reasons (on each tab):

10EC3CF5-F664-481F-BAE0-AD933DC0A009

Using IP Address:

With Signing Authentication via DocuSign password

I approve this document

Electronic Record and Signature Disclosure:

Accepted: 11/2/2020 2:09:16 PM

ID: 102e05f3-7156-49ba-9ce4-508e079f28ec

